To assess the effectiveness of this multilevel intervention, called the workplace *Metabolic Health Improvement Program (MHIP)*, we will conduct a double-randomized trial in partnership with the clinical trials division of a large Northern California-based academic healthcare system, Sutter Health ($N=700$ employees on $N=16$ hospital campuses). We will first cluster-randomize 8 Sutter Health hospital campuses to the SSB sales ban condition and 8 campuses to serve as controls (no sales ban). Across these 16 campuses, we will further randomize heavy-SSB-consuming employees (>30 oz/week) to receive a brief SSB counseling intervention delivered remotely or to a control condition.^{11,12} The **primary outcomes** are central obesity (e.g., waist circumference) and change in serum insulin sensitivity (homeostatic model assessment [HOMA] ratio). **Secondary outcomes** include changes in SSB consumption, Body Mass Index (BMI), and lab values to include: lipid profile, triglycerides, triglyceride:HDL ratio, uric acid, ApoA, ApoB, lactate, ALT/AST, GGT, fasting glucose, fasting insulin, HbA1c. We will assess dietary composition remotely using the Automated Self-Administered 24-hour (ASA-24) at baseline, 6 and 12 months, and waist circumference remotely with empirically validated instructions and a standardized tape measure provided to participants. We will collect blood samples in the workplace labs at baseline and 12 months. All analyses will consider compensatory changes in at-home SSB intake, calories from sugar, and total calories. Aims are:

Aim 1: How well does each intervention work alone? We will assess the independent effects of the brief counseling intervention and workplace SSB sales ban on changes in primary and secondary outcomes. We will compare outcomes across employees exposed to the brief intervention only ($n=175$), SSB sales ban only ($n=175$), and no intervention ($n=175$). *We hypothesize that the brief counseling intervention and sales ban will each independently decrease waist circumference and HOMA relative to no intervention. Those at high risk (baseline BMI >25 , ethnic-minority, and lower-occupational status) will benefit more from the interventions.*

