Aim 2: Does a multilevel intervention work better? We will assess the effects of combining a brief intervention and SSB sales ban on outcomes. We will compare outcomes for participants exposed to the multilevel intervention ($n=175$) to those who receive the: (a) brief intervention only ($n=175$), (b)

**SUTTER HEALTH
INSTITUTIONAL REVIEW BOARD**

Protocol Summary Form

sales ban only ($n=175$), and (c) no intervention ($n=175$). *We hypothesize that the combined intervention will have a greater effect on outcomes than the brief intervention or sales ban alone. Higher-risk employees (see Aim 1) will benefit more from the multilevel intervention than their lower-risk counterparts.*

Aim 3: (Exploratory): How does the intervention work? We will test whether changes in SSB cravings mediate the effects of the multilevel intervention on outcomes. The multilevel intervention seeks to increase motivation to reduce SSB intake while reducing environmental cues to drink SSBs. *We hypothesize that the multilevel intervention will lead to the greatest reductions in cravings for SSBs, and cravings will mediate its effects on outcomes. We will explore mediation across high-risk groups (see Aim 1).*

2. BACKGROUND:

Obesity and type 2 diabetes are pressing health concerns, particularly for lower-income and ethnic minority employees. Obesity rates are at an all-time high and disparities persist: 49.6% of adult African Americans are currently obese and 44.8% of Latinos, compared to 42.2% of non-Hispanic whites.¹³ Diabetes rates have nearly doubled since 2000.¹⁴ Employers face disproportionately rising obesity-related healthcare costs alongside productivity losses.¹⁵ Obesity is major concern for occupational safety, particularly for physically active nurses, manual workers and technicians at heightened risk for injury.^{15,16}

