Online Data Collection Evaluating UCSF Sales Ban: Observational data from an online survey of 2556 UCSF employees suggests that higher-risk demographic groups could disproportionately respond to the proposed intervention. Sample retention in this online study was 89% at the 12-month follow-up. Ethnic minority employees were twice more likely to report heavy consumption at baseline. Latinos experienced a more pronounced decline following the sales ban than Whites (by -3.7oz/day, $p < .007$). The lowest occupation stratum (service/manual workers) experienced a 30% reduction in consumption compared to 13% in the highest occupational group (academic medicine faculty) ($p < .0001$). *While limited by an observational approach, this study supports our proposed analyses by ethnic minority and lower occupational status, and speaks to our capacity for online data collection with good retention.*

Pilot Study of SSB Craving as a Mechanism: A published analysis of the UCSF pilot data found variable responses to the interventions for those with stronger SSB cravings (+1 SD above sample mean at baseline).¹² Individuals with weaker (-1 SD) SSB cravings reduced their SSB consumption, on average, by 12.8 oz/day ($p = .02$) more than individuals with stronger SSB cravings. However, among those with stronger cravings, those randomized to the multilevel intervention had significantly greater reductions in daily consumption (-19.21 oz/day vs. -2.49 oz/day, $p < .001$), a difference of 16.72 oz/day. *This study informs analyses proposed under Aim 3 by suggesting that employees with stronger SSB cravings may need the added motivational boost of brief counseling to achieve benefits on a par with others.*

Current Controlled Trial of Workplace Sales Ban in Sutter Health: In partnership with Sutter Health, we are currently completing a fully powered controlled trial of workplace SSB sales bans across 8 hospital campuses (5 intervention sites and 3 controls, $N = 657$ employees), funded by the [name] and John Arnold Foundation. Retention was 88% at 6 months and 78% at 12 (during the COVID-19 pandemic). Collection of anthropometrics for this controlled trial was interrupted by the pandemic, but we continue to collect dietary assessments and other data using an online format. At 6-months post-sales ban, there is a

**SUTTER HEALTH
INSTITUTIONAL REVIEW BOARD**

Protocol Summary Form

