statistically significant mean reduction of 4.2 oz/day in SSB consumption in employees at intervention sites versus controls ($p < .04$), including a 2.7 oz/day reduction in SSBs consumed while at work ($p < 0.02$). *This study is not cluster-randomized nor does it consider serum biomarkers for metabolic disease, which the proposed study will address. However, it demonstrates a successful collaboration with Sutter Health, and shows the feasibility of the proposed recruitment and remote data collection efforts.*

3. SIGNIFICANCE:

The proposed study tests a scalable, efficient approach for obesity prevention in the workplace. Following recent trials demonstrating the effectiveness of online obesity counseling using nonmedical providers, we test a remote counseling intervention delivered by trained health coaches.^{38,39} The SSB sales ban is a food environment intervention that is easily adopted through changes in procurement policy and that promotes health equity by impacting the workforce as a whole.

Across all aims of the proposed study, we will assess the heterogeneity of intervention effects across higher-risk employee groups from ethnic minority backgrounds, lower occupational status and >25 baseline BMI. A recognized limitation of this study is that our disparities analyses will be confined to people in the workforce. If the interventions tested here prove effective, however, future studies can test them in other congregate settings that touch populations outside the labor market (e.g., in criminal justice settings, community colleges).

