INSTITUTIONAL REVIEW BOARD**

Protocol Summary Form

counseling interventions, all found decreases in SSB consumption and BMI.⁴¹⁻⁴⁴ A pilot study and current trial by this team found that workplace sales bans reduce SSB consumption, waist circumference and some blood biomarkers for metabolic disease.¹¹

Analyses for all aims will also consider the hypothesis that those at highest risk for obesity and metabolic disease will benefit more from the interventions. This is justified by our pilot study showing that employees with a baseline BMI <25 benefitted most from the sales ban and brief intervention.¹¹ Preliminary studies (described above) suggest that ethnic minority and lower occupational status employees may experience disproportionate reductions in SSB consumption following an employer sales ban.

Analyses for all aims will also consider the possibility that study participants exposed to the interventions could compensate for reduced SSB consumption during work hours by increasing their consumption of SSBs at home, or by increasing calories from sugary foods or in the total diet.^{107,108} In our evaluation of the UCSF sales ban, we observed no compensatory at-home SSB consumption but rather, spillover effects of the intervention: After 12 months of exposure to a sales ban, the average SSB intake of heavy drinkers not only declined at work but also by 40% at home (by 9.3 oz/day) (data unpublished).

Research Design for Aim 1: The main analysis will focus on ANOVA and regression modeling to determine the independent effects of each intervention on primary and secondary outcomes.

Key Measures for Aim 1: As described in section C3d above: HOMA, waist circumference, abdominal adiposity, SSB consumption, insulin sensitivity, BMI, lipid profile, triglycerides, triglycerides:HDL ratio, liver function, glucose control, demographics, risk factors/disparities, and intervention assignment.

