Analytic Plan: We will analyze Aim 1 using all data collected at the baseline, 6- and 12-month time points. First, we will use ANOVA to compare group means and determine whether there is a significant main effect for each intervention (the sales ban and the brief intervention). Based on theory and our previous studies, we know that baseline risk factors and demographics are likely relevant to the impact of these interventions; those at greater baseline risk tend to benefit more from the interventions. Therefore, each dependent variable will also be examined using a linear regression model, which allows us to observe the main effects of these factors. For example, the model predicting HOMA change would include assignment to the sales ban condition (coded as 0/1), assignment to the brief intervention condition (coded as 0/1), baseline HOMA, baseline SSB consumption, baseline BMI, race/ethnicity, and sex. Subsequent models can consider baseline BMI > 25, ethnicity and job classification. The procedure for analyzing each outcome would be the same, but with each primary and secondary outcome substituted for HOMA in turn.

For SSB consumption, we will examine at-work consumption, at-home consumption, and total consumption as separate outcomes to thoroughly investigate the impact of the interventions across work and home environments. We will similarly check for potential compensatory consumption in sugar from calories and total calories for participants in the intervention conditions relative to controls. If ASA-24-based total calories or calories from sugar disproportionately increase in the intervention groups, this suggests a compensatory effect.

Although we believe our strategy of cluster randomization and controlling for individual differences that can vary regionally (such as ethnic distribution) is sufficient, we will also analyze the effects of the brief intervention via an exploratory mixed regression model, with individuals nested within sites, to see if study site was an important factor. If it is, we will consider mixed models where possible.

**SUTTER HEALTH
INSTITUTIONAL REVIEW BOARD**

Protocol Summary Form

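### Higher-risk employees are expected to benefit more, but the regression attached to that hypothesis gives only risk-factor main effects, and no intervention-by-risk term is specified for Aim 1 or Aim 2

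*Combined protocol and SAP*

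**What the plan says.** The hypothesis appears in four places.

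- **Section 1, Aim 1** names baseline BMI above 25 as the first risk marker and continues: "ethnic-minority, and lower-occupational status) will benefit more from the interventions".
- **Section 1, Aim 2** adds: "Higher-risk employees (see Aim 1) will benefit more from the multilevel intervention than their lower-risk counterparts".
- **Section 3 (Significance)** promises that, across all aims, "we will assess the heterogeneity of intervention effects across higher-risk employee groups".
- **Section 4c, Aim 1 Introduction** says the analyses for all aims will consider whether "those at highest risk for obesity and metabolic disease will benefit more from the interventions".

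The method is in the Aim 1 Analytic Plan of section 4c. That text repeats that people at greater baseline risk tend to gain more, and concludes from this that "each dependent variable will also be examined using a linear regression model, which allows us to observe the main effects of these factors". The example model for HOMA change contains the two assignment indicators, baseline HOMA, baseline SSB consumption, baseline BMI, race/ethnicity and sex. It has no product term. Then comes: "Subsequent models can consider baseline BMI > 25, ethnicity and job classification".

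The Aim 2 Analytic Plan repeats these models and adds one product term, sales ban × brief intervention. The risk variables remain covariates.

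**The concern.** Benefiting more is a statement about effect modification: the intervention effect in one risk group minus the intervention effect in the other. A main effect of a risk factor is a different quantity. It shows whether high-risk employees change more or less than others, averaged over arms.

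Followed as written, the plan yields no estimate and no test for a hypothesis stated under both Aim 1 and Aim 2. The form of the interaction, the coding of two of the three factors and the choice of contrast would be left until the data are available.

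**Working it through.** **1. Does any section supply the missing term?**

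| Place | What it offers | Intervention × risk term? |
|---|---|---|
| Section 2, online survey | Says that "this study supports our proposed analyses by ethnic minority and lower occupational status" | No method given |
| Section 3 | Intent to assess heterogeneity | No method given |
| 4c, Aim 1 example model | Risk variables as covariates | No |
| 4c, Aim 1 follow-up models | Three variables named | Form, coding and test not stated |
| 4c, Aim 2 model | Sales ban × brief intervention | No |
| 4c, Aim 3 | Intervention × craving change; high-risk group as a predictor | No |
| 4c, power statements (Aims 1 and 2) | Each intervention; ban × counselling | No |

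**2. Why a main effect cannot stand in.** Let P be the prognostic difference between risk groups without the ban, and D the extra ban effect in the high-risk group. With half the sample exposed to the ban, the risk coefficient in a main-effects model estimates P + D/2.

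- P = −0.20, D = 0 (no differential benefit): −0.20.
- P = 0, D = −0.40 (substantial differential benefit): 0 + (−0.40)/2 = −0.20.

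The two situations give the same coefficient. Simulation agrees. With a true ban-by-risk interaction of −0.48 SD and nothing else, the main-effects model returned about −0.24 for the ban and −0.24 for risk. A model with the product term detected the interaction in about 81% of 2,000 runs.

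**3. What the added terms could detect.** The plan gives no figure for a risk interaction, so there is none to reproduce. From the plan: 550 at 12 months, about 138 per cell, alpha .05, 80% power. Assumed: a two-sided test, a high-risk share p of 0.5 or 0.2, and a between-campus SD of the factor effect (τ) of 0 or 0.2. All results are in outcome SD units.

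- *Benchmark, main effect of one intervention:* 2.80 × 2/√550 = 0.24.
- *Standard error of an interaction:* SE = 2/√(N·p·(1−p)).
- *Counselling × factor* (within campus, N = 550): p = 0.5, SE 0.171, detectable 2.80 × 0.171 = **0.48**; p = 0.2, SE 0.213, detectable **0.60**.
- *Terms comparing ban with non-ban campuses* (8 versus 8): variance = SE² + τ²(1/8 + 1/8) = SE² + τ²/4. The multiplier on 14 df is 2.145 + 0.868 = 3.013.

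| Term | N | p | τ = 0 | τ = 0.2 |
|---|---|---|---|---|
| Ban × factor | 550 | 0.5 | 0.51 | 0.60 |
| Ban × factor | 550 | 0.2 | 0.64 | 0.71 |
| Combined vs none × factor | 276 | 0.5 | 0.73 | 0.79 |
| Combined vs none × factor | 276 | 0.2 | 0.91 | 0.96 |

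**4. Power in a plausible case.** Suppose each component gives high-risk employees an extra 0.20 SD, additively, with half high risk (all assumed). The difference for combined versus none is then 0.20 + 0.20 = 0.40. On 14 df, power is 34% at τ = 0 and 30% at τ = 0.2.

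**5. Why campus matters here.** In a simulation with 16 campuses, no true interaction and τ = 0.2, a test of ban × risk that ignored campus rejected in 9.8% of trials. A campus-level test on 14 df rejected in 5.5%.

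**6. Number of terms.** Three terms (ban, counselling, combined versus none) × 3 factors × 2 primary outcomes = 18. At .05 each, the chance of at least one false positive would be 1 − 0.95¹⁸ = 0.60 if the terms were independent. They are not: in balanced cells the combined-versus-none interaction equals the sum of the other two.

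**The case against.** The authors have a fair reply. The HOMA model is offered as an example, and it already contains baseline BMI and race/ethnicity. A further set of models naming BMI above 25, ethnicity and job classification would add little as plain adjustment, so those may well be the intended moderation models. That is plausible, and the intent stated in Significance supports it. But the sentence that draws the method from the hypothesis speaks of main effects, the follow-up models are optional and have no terms, and the Aim 2 text shows that the authors write out a product term when they want one.

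Several stronger readings are tempting but not supported.

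- *That the authors will report a risk-factor coefficient as differential benefit.* No section says so.
- *That everything about the subgroup analysis is open.* The three factors, the BMI cut-point and the Aim 2 comparisons are all named. What remains open is the model term and the coding of ethnicity and occupational status. Even that coding may exist elsewhere: the Aim 1 key measures refer to a section C3d, which is not in the supplied text.
- *That each Aim 2 comparison needs its own factor interaction.* The Aim 2 risk hypothesis concerns benefit from the multilevel intervention, and combined versus none tests it directly. Adding combined versus each single intervention would give five terms per factor on three degrees of freedom, which raises the test count for little information.

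It can also be said that an analysis this imprecise is hardly worth specifying. Low precision is a reason to label it exploratory. It does not justify leaving a stated hypothesis without an estimate.

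**Conclusion.** The concern holds. The hypothesis is about effect modification, the model attached to it contains only main effects, and no other section supplies an intervention-by-risk term for Aim 1 or Aim 2. This conclusion rests on the text and needs no numerical assumption.

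The detectable differences do rest on assumptions, because the documents give neither the high-risk shares nor the between-campus variation. On the ranges used, they are two to four times the 0.24 SD benchmark for an intervention main effect (0.48/0.24 = 2; 0.96/0.24 = 4).

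The point is worth correcting but limited in reach. A reader might infer that the main ban and counselling comparisons are compromised; nothing in this point touches them.

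**What to change.** - **Aim 1 Analytic Plan:** replace the main-effects sentence with prespecified sales ban × factor and counselling × factor terms for the three named factors.
- **Aim 2 Analytic Plan:** add the factor interaction for combined versus no intervention, as the direct test of the Aim 2 risk hypothesis.
- **Coding:** fix the categories for ethnicity and occupational status before the data are seen, or include the definitions if section C3d holds them.
- **Campus:** for terms that compare ban with non-ban campuses, account for the 16 randomised campuses with small-sample degrees of freedom.
- **Reporting:** give interaction estimates with confidence intervals, labelled exploratory, and state that a null interaction does not show equal benefit.

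The cost is plan wording and extra model terms on baseline data already scheduled for collection. The downside is the low precision and a set of 18 terms in which some chance findings are likely.

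As a separate wording matter, the Aim 1 Introduction in section 4c says pilot benefit was greatest at baseline BMI below 25, while the pilot summary in Background says above 25. The two statements should be reconciled.

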Public health impact: If effective, the proposed employer-sponsored multilevel intervention will offer an efficient, scalable strategy for preventing obesity in millions of American working adults. This study will also contribute to science on mechanisms of change in obesity prevention and inform the design of interventions that exploit synergies between individual behavior change strategies and food environment policies.

4. METHODS:

(4a) General Study Design:

This is a prospective, double-randomized study in which 16-Sutter Health affiliate hospital campuses will be cluster randomized to control (no SSB sales ban) vs. intervention (removal of SSBs). Across these 16 campuses, we will enroll 700 employees and then randomize those who self-report consuming >30 oz of SSB per week to receive a brief counseling intervention or control (no intervention).

**SUTTER HEALTH
INSTITUTIONAL REVIEW BOARD**

Protocol Summary Form

(4b) Procedures:

Cluster Randomization of 16 Sutter Health Affiliates

Sutter Health affiliates will be eligible to participate in the study who meet the criteria: 1) the affiliate has not participated in a SSB intervention; 2) the affiliate is not in a county that has instituted a SSB sales tax. Affiliates will be stratified by their location (urban vs. rural) and number of employees and will be randomly assigned using a computer program to be assigned to either control or intervention. Sutter Health leadership ([name] and [name]) have signed a letter of support to conduct this study.

Sites randomized to the SSB will eliminate sugar-sweetened beverages from the cafeterias, vending machines, Walgreens, vendors, and from patient care areas. Sutter Health has already implemented Healthy Beverage Initiatives (HBI) at Alta Bates, Palo Alto Medical Foundation (PAMF) and all CPMC campuses.

Study Procedure	Description	Baseline	6 Months	12 Months
Informed Consent	Procedures Described Below	X		
Demographics	Self-reported gender, ethnicity, household income, education, work location, hours, shifts	X	X	X
Medical History	Self-reported concurrent medications and general medical history with an emphasis on diabetes	X	X	X
Height	Measured using a stadiometer on a standardized scale at a semi-private location on the affiliate campus.	X		
Weight	Obtained on a standardized scale at a semi-private location on the affiliate campus.	X	X	X

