Copenhagen Burnout Inventory (CBI): The 6-item portion of the CBI assess personal burnout as is a state of prolonged physical and psychological exhaustion. Participants quantify the frequency of physical and emotional fatigue, as well as their susceptibility to illness, from on a six-point scale from "Always" to "Never". Formulated in a way that all human beings can answer it (regardless of job status), the measure was validated through the PUMA study.

Participant Randomization

Upon completion of five enrollment measurements (questionnaires, height/weight, waist, ASA24, and blood draw) participants will be randomly assigned to either a control group, or a group receiving a brief, remote motivational intervention, known as the Metabolic Health Improvement Plan (MHIP). Participants are randomized by a REDCap randomization module, using stratified random sampling by location. Those randomized to intervention will be contacted as described below.

SSB Brief Motivational Counseling Intervention- The Health Improvement Program

Participants randomly assigned to the health improvement program and will be contacted to participate in an education session with a trained coach via phone or video conference. The session led by a trained coach will describe the amount of sugar ingested in SSBs per week and will then proceed to provide personal guidance on health risks and the benefits of reducing sugar intake. Next, the coach will engage the participant in achievable, gradual goals to reduce SSB consumption reviewing and providing education materials. This will include discussing substitution beverages and preferred alternatives. Coaches will provide tools to the participant to increase self-efficacy and mediate the impact of stress, and cravings. The brief counseling session ends with the coach providing education materials including recordings relevant to the discussion, which can include topics of stress reduction and mindfulness. Depending on the participant, the brief intervention will take between 15 and 25 minutes to complete.

The coach will make two, 5-minute booster telephone calls within 4-6 weeks of the initial call. The first will be about two weeks after the initial session and the second call will be about two weeks later. The coach will revisit goals and obstacles and determine compliance to the educational materials.

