Analytic Plan for Aim 2: Having established the main effects of each intervention under Aim 1, our analyses for Aim 2 focus on the interaction between them. Specifically, we anticipate that the combined intervention will have an effect above and beyond the simple additive effects of the two interventions. This analysis will require replicating the ANOVA and regression models used for Aim 1 with the addition to each of an interaction term for the two interventions. For example, the model predicting HOMA change will include assignment to the sales ban condition (coded as 0/1), assignment to the brief intervention condition (coded as 0/1), the interaction term for the two conditions (sales ban*brief intervention), baseline HOMA, baseline SSB consumption, baseline BMI, race/ethnicity, job classification (if sample size allows, as above), and sex. The procedure for analyzing each outcome is the same, but with each primary and secondary outcome substituted for HOMA in turn. This time, the main variable of interest will be the interaction term. We will graph and deconstruct each significant interaction term to determine the details of the interaction.

Power Calculations: As with Aim 1 above, power calculations are based on findings from the UCSF pilot and retention rates from the Sutter pilot. We will have 175 participants in each of the following groups. With 80% retention, this allows a final N of 550, with approximately 138 in each of the four experimental conditions. Power analysis for a full factorial design conducted with the BDEsize¹⁰⁹ package within R¹¹⁰ indicates that at 80% power and an alpha level of .05 we will be able to detect effect sizes as small as .12 for the interaction between the two interventions.

Anticipated Problems and Alternative Approaches: As with Aim 1, attrition and self-report bias are the primary potential issues we anticipate; handling of each is described above.

Expected Outcomes: We anticipate a significant interaction term, and more specifically, that the effect of the sales ban and brief intervention together will be stronger than each is individually. Participants assigned to the brief intervention and working at sites with a sales ban would thus demonstrate the greatest amount of change, and more change than one would expect if the effect of the two conditions were simply additive.

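### The randomisation strata appear in no Aim 1 or Aim 2 model, and the sales ban is tested with no campus error term; the ban's standard error is too small, and adding the strata alone does not cure it

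*Combined protocol and SAP*

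**What the plan says.** Section 1 sets the allocation: "We will first cluster-randomize 8 Sutter Health hospital campuses to the SSB sales ban condition and 8 campuses to serve as controls". Section (4b), on cluster randomisation, adds: "Affiliates will be stratified by their location (urban vs. rural) and number of employees and will be randomly assigned using a computer program". The number of size categories and their cut-points are not given. Section (4b), Participant Randomization, then allocates employees to counselling or control "using stratified random sampling by location", without saying whether location there means campus or the urban/rural split.

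In section (4c), the Aim 1 Analytic Plan begins at the level of the individual: "First, we will use ANOVA to compare group means and determine whether there is a significant main effect for each intervention". The regression that follows has the ban indicator plus "assignment to the brief intervention condition (coded as 0/1), baseline HOMA, baseline SSB consumption, baseline BMI, race/ethnicity, and sex". Later Aim 1 models go no further towards the strata: "Subsequent models can consider baseline BMI > 25, ethnicity and job classification". The Aim 2 regression adds "the interaction term for the two conditions (sales ban*brief intervention), baseline HOMA, baseline SSB consumption, baseline BMI, race/ethnicity, job classification" and sex.

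The only Aim 1 or Aim 2 model with employees nested in sites is exploratory and is described for the counselling effect. Wider use of mixed models is left as something to consider if site turns out to matter, with no ban model or covariates specified.

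**The concern.** An analysis should reflect how the trial was randomised, and here two features are missing for the ban.

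- **The unit of allocation.** The ban varies only between campuses, so its real information comes from 8 against 8 campus means. An individual-level ANOVA or regression takes its error from employee-to-employee variation and has nowhere to put campus-to-campus variation.
- **The strata.** Balancing campuses on setting and size lowers the true variance of the ban estimate. A campus-level standard error reflects this only if the strata are in the model.

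At stake is the type I error of the ban effect on waist circumference and HOMA, the co-primary outcomes. The two omissions pull in opposite directions, so they have to be repaired together.

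**Working it through.** **Inputs from the documents.** 16 campuses, 8 per arm; 550 retained at 12 months; alpha .05 (two-sided assumed); models as listed in (4c). Average campus size m = 550/16 = 34.4.

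**Assumptions (not in the documents).** ICC .03 to .05; share s of between-campus variance explained by strata 30 to 50%; four strata of four campuses, two per arm in each; equal campus sizes; total variance 1.

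**The plan's own figures.** 700 × 0.80 = 560, against 550 stated; 550/4 = 137.5, stated as about 138. The detectable interaction of .12 reproduces as Cohen's f with 550 independent people: noncentrality 550 × .12² = 7.92 on 1 and 546 df gives 80.2% power. The .08 for main effects does not reproduce as f (47% power) or d (15%). Its metric is undefined, which is a separate matter. No allowance for clustering is stated.

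**Step 1. The ban under the planned model.**
Model SE ≈ √(4/550) = .0853.
True SE = √(2v/8), where v = ICC(1−s) + (1−ICC)/34.4.
Approximate size = 2Φ(−1.96 × model SE / true SE).

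| ICC | s | v | True SE | Model/true | Size, formula | Size, simulated | Simulated, strata added |
|---|---|---|---|---|---|---|---|
| .03 | 30% | .0492 | .1109 | 0.77 | 13.2% | 13.0% | 13.2% |
| .03 | 50% | .0432 | .1039 | 0.82 | 10.8% | 10.6% | 10.9% |
| .05 | 30% | .0626 | .1251 | 0.68 | 18.2% | 18.4% | 18.9% |
| .05 | 50% | .0526 | .1147 | 0.74 | 14.5% | 14.1% | 14.8% |

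Over a wider grid (ICC .01 to .05, s from 0 to 75%) simulated size runs from 5.9% to 23.4%. It exceeds 5% in every setting. The model SE is too small whenever ICC(1−s) exceeds ICC/34.4, that is, unless the strata explain more than about 97% of the between-campus variance.

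**Step 2. A campus-level analysis of the ban, without and with strata (simulated).**

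| ICC | s | Size without strata (14 df) | Size with strata (11 df) | Power at d = 0.24, without → with |
|---|---|---|---|---|
| .03 | 30% | 3.3% | 5.0% | 44% → 50% |
| .03 | 50% | 2.3% | 5.1% | 43% → 56% |
| .05 | 30% | 2.9% | 5.0% | 34% → 42% |
| .05 | 50% | 1.7% | 4.9% | 32% → 48% |

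**Step 3. Price if the strata explain nothing.** The critical t rises from 2.145 (14 df) to 2.179 (12 df, two additive binary factors) or 2.201 (11 df, four full strata). The ratios 1.016 and 1.026 give an interval about 2 to 3% wider. At ICC .03, power at d = 0.24 falls from 46% to 44% with 11 df.

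**Step 4. Counselling.** If location means campus, counselling is balanced within campus and campus differences cancel from its true error, but a model without campus keeps them in the residual. Model SE / true SE ≈ 1/√(1−ICC): 1.015 at ICC .03 and 1.026 at ICC .05.

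**The case against.** A reader might infer from the missing strata that the planned regression overstates the ban's error, giving too wide an interval and a test that rejects less than 5% of the time. The documents do not support that. Overstatement needs a model that charges campus differences to a campus error term, and the planned ANOVA and regression have none. Step 1 shows the opposite sign. A reader might also infer that the precision gained by stratifying is thrown away. It is not: balance still lowers the true variance of the estimate, and only its recognition in the standard error is at issue.

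The best defence of the plan is that it already adjusts for baseline outcome, BMI and race/ethnicity, partly because these vary by region, and that it leaves mixed models open. The first part has some force: such covariates may absorb part of the between-campus variance, and part of what the strata would explain. The calculations ignore this, and the ICC and the share explained are assumed. But individual covariates do not supply a campus error term. The nested model is exploratory and aimed at counselling, and the conditional extension names no ban model. If it were taken up with a campus random effect alone, the test would move from anti-conservative to conservative.

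It also stands that the counselling effect and the Aim 2 interaction are largely within-campus contrasts, in which campus intercepts cancel. The inflation concerns the ban effect.

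**Conclusion.** The omission is established from the text: the trial stratifies at both levels, and no Aim 1 or Aim 2 model carries the strata. The larger consequence for the ban comes from the absent campus error term. Size is about 11 to 18% instead of 5% at ICC .03 to .05 with strata explaining 30 to 50% of between-campus variance, and adding strata alone does not change that. Once campus is the unit of inference the strata do matter: without them size is about 2 to 3%, with them about 5%. For counselling the effect is minor, a standard error about 2 to 3% too wide, and only if location means campus.

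The direction for the ban holds for any positive ICC unless the strata explain almost all the between-campus variance. The sizes depend on the assumed ICC, share explained, stratum layout and equal campuses. The conclusion that the planned regression overstates the ban's error should not be drawn.

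**What to change.** 1. In every Aim 1 and Aim 2 model with the ban term, make campus the unit of inference: a campus random effect with small-sample degrees of freedom, or an analysis of campus-level summaries. Make this the main analysis, not a conditional one.
2. In those same models include urban/rural setting and the workforce-size stratum as fixed campus-level covariates. State the number of size strata and their cut-points.
3. Define location in the employee randomisation, and include campus (or whatever location denotes) in the counselling contrast.

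The cost is wording in the analysis plan, settled before outcome data are seen, and two or three campus-level degrees of freedom (14 down to 12 or 11). Ban intervals will also be wider than the planned regression would print, because that regression understates the error.
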